9.4 Other drug utilisation for MDD

The following will be summarized for treatments other than Seroquel XR for MDD the daily dose at the first initiation, whether a dose change accompanied initiation of Seroquel XR, latest dose following Seroquel XR initiation, interval from initiation of Seroquel XR to latest dose change and whether the prescription was continuing on the index date.

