9.3 Seroquel XR utilisation

At the time of initiation of Seroquel XR, the diagnosis for which Seroquel XR was prescribed, whether the patient was experiencing psychotic symptoms, Clinical Global Impression, the initial daily dose of Seroquel XR prescribed and any concomitant antidepressant drug(s) and dose(s) prescribed will be summarized descriptively by country and overall.

The last prescribed daily dose prior to the index date, the maximum daily dose prescribed, modal daily dose, and the duration for each dose of Seroquel XR as prescribed will be summarized descriptively by country and overall.

Doses described above will be summarized in two ways.

- As continuous variable: the following will be calculated: number mean, mode, median, minimum, maximum, and standard deviation
- As a categorical variable: number and % of patients will be provided for each of the following dose levels: 50 mg, 100 mg, 150 mg, 300 mg and other.

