 Yes  No  Unknown	 Yes  No  Unknown

MDD Treatment

This section is dedicated to recording **drug treatments** received by this patient for his / her MDD in the **12 months up to [INDEX DATE]**.

In the table below, please list **ALL drug treatments for MDD** that started and ended before the initiation of Seroquel XR received by the patient in the 12 months up to [INDEX DATE]. **Please include any drug treatments for MDD noted in the patient's medical record that were prescribed either by the investigator or by other physicians.** Also, for each drug treatment, please specify information on start and end date and dosing. Please record **all changes in dose** as separate line entries.

(1) Specific drug name (generic or brand names)	(2) Start date (day/mth/year) Check for "on demand" or prn use	(3) End Date (day/mth/year)	(4) Dose (specify Unit)
	-- / / --  prn	-- / / --	_____
	-- / / --  prn	-- / / --	_____
	-- / / --  prn	-- / / --	_____
	-- / / --  prn	-- / / --	_____
	-- / / --  prn	-- / / --	_____
	-- / / --  prn	-- / / --	_____

In the table below, please list **ALL drug treatments for MDD** that were **prescribed concurrently with Seroquel XR** (including Seroquel XR) received by the patient in the 12 months up to *[INDEX DATE]*. **Please include any drug treatments for MDD noted in the patient’s medical record that were prescribed either by the investigator or by other physicians.** Also, for each drug treatment, please specify information on start and end date (if applicable), dosing and dates of dose changes.

For Seroquel XR prescriptions, please record all changes in dose as separate line entries using columns (1) – (4).

Instructions: Please answer these questions for ALL drug treatments for MDD that were prescribed by the investigator or other physicians concurrently with Seroquel XR For Seroquel XR, please record all changes in dose as separate line entries
				
Instructions: Please answer these questions only for drug treatments for MDD that were prescribed by the investigator or other physicians concurrently with Seroquel XR
		

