(1) Specific drug name (generic or brand names)	(2) Start date (day/mth/year) Check for “on demand” or prn use)	(3) End Date (day/mth/year)	(4) Dose (specify Unit)	(5) Did the dose change at initiation of Seroquel XR?	(6) Most recent dose prior to [INDEX DATE] (if different than at initiation)	(7) Date of most recent dose change (day/mth/year)
	___/___/___  prn	___/___/___  Still prescribed at [INDEX DATE]	_____	 Increase  Decrease  Remained the same  Not applicable	_____  Not applicable	___/___/___  Not applicable
	___/___/___  prn	___/___/___  Still prescribed at [INDEX DATE]	_____	 Increase  Decrease  Remained the same  Not applicable	_____  Not applicable	___/___/___  Not applicable
	___/___/___  prn	___/___/___  Still prescribed at [INDEX DATE]	_____	 Increase  Decrease  Remained the same  Not applicable	_____  Not applicable	___/___/___  Not applicable
	___/___/___  prn	___/___/___  Still prescribed at [INDEX DATE]	_____	 Increase  Decrease  Remained the same  Not applicable	_____  Not applicable	___/___/___  Not applicable

Seroquel XR Treatment

Was the patient experiencing psychotic symptoms at initiation of Seroquel XR?

- Yes
- No
- Unknown

Which disorder was Seroquel XR prescribed for?

Please select all that apply

- MDD
- Schizophrenia
- Bipolar disorder
- Other – please specify _____

How many times has the investigator seen this patient since initiation of Seroquel XR?

__ visits

What is your estimate of patient adherence to the prescribed treatment regimen that included Seroquel XR for depression?

___ % of time adherent to prescribed dose(s) (range: 0 – 100%)

(Investigator assessment)

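### In the concurrent-drug table, one dose column with no stated time point must supply both a drug's first dose (Section 9.4) and its dose at Seroquel XR start (Section 9.3), so one of the two can be lost when the dose changed up to that start

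*Protocol*

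**What the plan says.** Protocol Section 9.3 describes the situation when Seroquel XR is started. At that time point, "any concomitant antidepressant drug(s) and dose(s) prescribed will be summarized descriptively by country and overall".

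Protocol Section 9.4 covers MDD treatments other than Seroquel XR. It lists "the daily dose at the first initiation, whether a dose change accompanied initiation of Seroquel XR", then "latest dose following Seroquel XR initiation, interval from initiation of Seroquel XR to latest dose change", and whether the drug was still prescribed on the index date.

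The source of these data is the concurrent-drug table in Appendix B (MDD Treatment). After drug name, start date and end date, its columns are:

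- "4) Dose (specify Unit"), with no time point given;
- "5) Did the dose change at initiation of Seroquel XR", answered by direction only (increase, decrease, same, not applicable), with no amount;
- "6) Most recent dose prior to [INDEX DATE] (if different than at initiation");
- column 7, one date, that of the latest dose change.

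The rule on extra lines in this table is limited to one drug: "For Seroquel XR prescriptions, please record all changes in dose as separate line entries". The preceding table does ask for every dose change on its own line, but it takes only drugs that were already stopped when Seroquel XR began.

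**The concern.** Sections 9.3 and 9.4 together call for three doses of each concurrent drug: at its own start, at Seroquel XR start, and latest. The form has two dose fields, and the second is reserved for the latest dose. Column 4 therefore has to stand for both of the earlier doses, and the form does not say which it is.

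The layout points both ways. Column 4 sits beside the drug's own start date, which suggests the first dose. Column 6 says "if different than at initiation" directly after a column about the initiation of Seroquel XR, which suggests that the reference value in column 4 is the dose at that event.

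An objective in Section 1.1 is to describe differences between countries in treatment practices involving Seroquel XR. If monitors in different countries read column 4 differently, the background-dose summaries would mix time points, and part of any difference between countries could come from the form.

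**Working it through.** The protocol gives no figure to reproduce. The check is whether the form, completed as written, determines both planned doses.

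**Set-up.** Take a concurrent drug started before Seroquel XR and entered on one row. Let d0 be its dose at its own start, dS its dose at Seroquel XR start (after any change made then), and dL its latest dose before the index date. The dose may or may not change before, at, and after Seroquel XR start. That gives 2 × 2 × 2 = 8 histories, 7 of them with a change. Section 9.4 needs d0 and dL; Section 9.3 needs dS.

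**Reading A: column 4 = d0.** Column 6 then gives dL where it differs from d0, and column 7 dates the last change. If that date is on or before Seroquel XR start, dS = dL and is known. If it is later, dS is an intermediate value with no field.

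**Reading B: column 4 = dS.** Column 6 gives dL. No field holds d0. Column 5 gives only the direction of a change at Seroquel XR start, so d0 cannot be worked back from dS.

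| Dose changed | Reading A | Reading B |
|---|---|---|
| never | both known | both known |
| after only | d0 = dS, column 4 right | d0 = dS, column 4 right |
| before only | both known | d0 lost |
| at only | both known | d0 lost |
| before and at | both known | d0 lost |
| before and after | dS lost | d0 lost |
| at and after | dS lost | d0 lost |
| before, at and after | dS lost | d0 lost |

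The two doses can differ in the last 6 rows. One planned output is lost in 3 of these 6 under reading A (always the Section 9.3 dose) and in 6 of 6 under reading B (always the Section 9.4 first dose). These count patterns; they are not frequencies.

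**Two further points.** First, in the after-only row column 4 holds the right value, but the entries cannot rule out an earlier change as well, so the analyst cannot separate that row from before-and-after.

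Second, the recovery under reading A needs column 6 to be compared with d0. A monitor who enters d0 in column 4 but takes column 6 to refer to Seroquel XR start would mark it not applicable when nothing changed afterwards, and dS is lost in those rows too. For the same reason, the pattern of entries is not a reliable guide to which reading was used.

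**Size in general terms.** Let p be the share of these drugs whose dose changed between their own start and Seroquel XR start (inclusive), and q the share of those that changed again before the index date. The share of entries losing a planned dose is p × q under reading A with column 6 read consistently, and p under reading B. The documents give neither p nor q. Since q lies between 0 and 1, the loss under A runs from 0 to p.

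**After the fix.** With both doses in labelled fields, or one dated line per dose, d0 and dS are determined in 8 of 8 histories.

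**The case against.** The best defence is that reading A is the natural one. Columns 1 to 4 repeat the layout of the preceding table, where the dose belongs to the start date. On that reading the columns match Section 9.4 item by item: first dose, change at Seroquel XR start, latest dose, date of latest change, still prescribed. Only the Section 9.3 dose is then at risk, and only where at least two changes occurred with the last one after Seroquel XR start. This stands, and it limits the loss. It does not settle the reading, because neither column 4 nor column 6 states it.

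A reader might infer something stronger: that the table has a single dose column, so one output is lost whenever the dose changed. The form does not support that. Column 6 is a second dose field, column 7 allows recovery in three patterns under reading A, and a change only after Seroquel XR start loses nothing. Nor do the documents support any stated percentage of unrecoverable entries. Monitors have direct access to the original records, so a missing dose could be looked up again if someone noticed the need.

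There are mitigating provisions. The table's general instruction asks for doses and change dates for each drug. Section 5.1 provides scripts and trained abstractors, Section 8.1 provides manual review and queries, and the questionnaire may be revised after the pilot. These make it wrong to say that monitors will certainly diverge. They do not close the gap: the columns hold one change date, the separate-line rule names only Seroquel XR, and training cannot fill a field that does not exist.

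Finally, the analysis is descriptive, and Section 5 singles out the Seroquel XR dose as of particular interest. That dose is captured line by line. The concern is confined to the background drugs.

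**Conclusion.** The concern holds in a limited form. Column 4 is the only field for two planned doses, its time point is undefined, and column 6 does not say whose initiation it means. Where the dose changed up to Seroquel XR start, the form can lose the Section 9.3 dose (3 of 6 patterns, reading A) or does lose the Section 9.4 first dose (6 of 6, reading B). With readings mixed, each summary could combine doses from different time points, unevenly across monitors and countries.

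This rests on three assumptions: one row per non-Seroquel drug, as the instructions imply; first initiation in Section 9.4 meaning the drug's own start, which fits that section's naming of Seroquel XR when it means that event; and column 7 accepting a date on or before Seroquel XR start. How many entries are affected cannot be stated from the documents.

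It is more than a detail left to an analysis plan. No analysis rule can supply a dose that was not collected, and Section 9 rules out imputation.

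**What to change.** Make one of two changes to the concurrent-drug table in Appendix B:

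- require a dated separate line for every dose change of every concurrent MDD drug, as the form already does for Seroquel XR and for drugs stopped earlier; or
- split column 4 into the dose at first start of this drug and the dose at Seroquel XR initiation.

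In either case, state in column 6 which initiation is meant, and use the same terms in Sections 9.3 and 9.4.

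The cost is one added eCRF field or a changed instruction, and slightly more abstraction time. Sections 4.1.2 and 4.2.2 already allow the questionnaire to be revised after the pilot and on the advisory board's recommendation. The documents do not show whether the pilot has been run. If abstraction has already begun, the affected rows would have to be checked again against the medical records.

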10. SAFETY EVENT REPORTING

10.1 Safety Reporting for Investigators

Due to the non-interventional and retrospective design of this drug utilisation study, adverse event (AE), serious adverse event (SAE) and other safety data are not proactively collected. Instead investigators should report any adverse events noted during routine medical practice according to the standard spontaneous reporting procedures for marketed products in their country. The questionnaire associated with this study should not be used to record or report adverse event data.

If there are any questions regarding AE and SAE reporting obligations, the local AstraZeneca representative should be contacted.

Appendix B**

Drug Substance	SEROQUEL [®] XR
Study Code	D1443C00057
Edition Number	3
Date	██████████

**Appendix B
Drug Utilisation Questionnaire**

Doctor Information – MDD Survey

Instruction for completion: The following are general questions about you and your practice. Please answer to the best of your knowledge.

General Demographics

What country do you practice in?

What region do you practice in?

What city or town do you practice in?

What is your gender?

Male

Female

What is your year of birth?

How long have you been in practice as a medical doctor?

__ _ years

How long have you been working in your current speciality?

__ _ years

Practice Details

If you now think about the practice from which you are selecting patient records for this study:

How would you describe the location from which you are selecting patient records for this study?

Select one answer only.

Urban centre

Suburban

Rural

Please select out of the following options the one that best describes this setting:

Select one only.

General Hospital (public & private)

University Hospital

Mental health centre

Other open care facilities (ambulatory, out-patient clinic, community clinic)

Private office

Mixed (hospital & office/community/clinic):

Other – Please specify

In this setting, what proportion of patients are diagnosed with MDD ___%

What proportion in this setting are in-patients?

___%

The following two questions are to be answered for physician practices that are based in a hospital setting:

Could you specify the total number of hospital beds in the hospital where you spend the majority of your time?

_____ beds

Could you specify the number of beds that are dedicated to psychiatry?

_____ beds

Location of Medical Record

Please select the location that the patient's medical record for this study is from:

- outpatient clinic or private practice
- hospital or in-patient setting
- other specify:

Patient Form – MDD Survey - To be completed by data extraction monitor unless indicated as ‘Investigator Assessment’

Instructions for completion: Please respond to the following questions about patients prescribed Seroquel XR treatment for MDD at any time between *date 1 and date 2 [INDEX DATE]*. Additional detailed instructions provided in other sections of this questionnaire.

General Patient Demographics

What is the patient’s month and year of birth?

__ / __
mo / year

What is the patient’s gender?

- Male
- Female

What is the patient’s height?

__ cm
 Unknown

If you have specified a height for this patient, has it been:

- Measured?
- Estimated?
- Not specified?

What was the patient’s weight at the visit closest to *date 1 (date 1 = 9 months prior to [INDEX DATE])*

__ kg
 Not specified?

Date that weight was:

- measured?
- reported by patient ?
- not specified?

__ / __ / __
day / mo / year

What is the race of this patient?

- White
- Black
- Asian
- Other (including native people or mixed races) – please specify _____
- Not specified

Referral Pathways

When did the investigator see this patient for the first time?

__ / ____ (month / year)

mo / year

Who referred this patient to the investigator?

Please select one answer only

- Primary care physician
- Another psychiatrist (in-patient)
- Another psychiatrist (out-patient)
- Law enforcement
- Family member
- Accident & emergency
- Social services
- Self-referral
- Other – please specify _____

Why was this patient referred to the investigator?

Please select all that apply

- Specific need for psychiatric care
- Access to specific treatments
- Severity of MDD
- Concomitant disorders / complexity of psychiatric state
- Other – please specify _____

Medical/Psychiatric History

In the table below, please record if, according to the medical record, the patient has ever reported/experienced any of the following concomitant disorders? *Please select all that apply*
 Has the patient received **drug treatment** (in the past or current) for any of these conditions?

Please select all that apply

	Ever Experienced	If experienced, is the condition past /current Circle all that apply?	Received Drug treatment (in the past)	Receiving Drug treatment (currently)
Anxiety disorder(s)	Yes / No / Unknown	Past / Current	Yes / No / Unknown	Yes / No / Unknown
Alcohol abuse	Yes / No / Unknown	Past / Current	Yes / No / Unknown	Yes / No / Unknown
Nicotine use	Yes / No / Unknown	Past / Current	Yes / No / Unknown	Yes / No / Unknown
Illicit substance abuse	Yes / No / Unknown	Past / Current	Yes / No / Unknown	Yes / No / Unknown
Other Axis 1	Yes / No / Unknown Please specify 1) _____ 2) _____ 3) _____	Past / Current Past / Current Past / Current	Yes / No / Unknown Yes / No / Unknown Yes / No / Unknown	Yes / No / Unknown Yes / No / Unknown Yes / No / Unknown
Other Axis 2	Yes / No / Unknown Please specify 1) _____ 2) _____ 3) _____	Past / Current Past / Current Past / Current	Yes / No / Unknown Yes / No / Unknown Yes / No / Unknown	Yes / No / Unknown Yes / No / Unknown Yes / No / Unknown
Hypertension	Yes / No / Unknown	Past / Current	Yes / No / Unknown	Yes / No / Unknown
Obesity	Yes / No / Unknown	Past / Current	Yes / No / Unknown	Yes / No / Unknown
Dyslipidemia	Yes / No / Unknown	Past / Current	Yes / No / Unknown	Yes / No / Unknown
Other cardiovascular	Yes / No / Unknown Please specify 1) _____ 2) _____ 3) _____	Past / Current Past / Current Past / Current	Yes / No / Unknown Yes / No / Unknown Yes / No / Unknown	Yes / No / Unknown Yes / No / Unknown Yes / No / Unknown
Diabetes	Yes / No / Unknown	Past / Current	Yes / No / Unknown	Yes / No / Unknown

Diagnosis of MDD

What was the date of the **1st depressive episode** experienced by this patient (if known)?

___/_____
mo / year

Unknown

What was the date of **diagnosis of MDD?**

___/_____
mo / year

Unknown

Who initially diagnosed this patient with MDD?

Please select one answer only

The investigator

Another psychiatrist

Primary care physician

Other specialist – please specify _____

Unknown

How many **depressive episodes** has this patient experienced in his / her lifetime?

0

1

2

3 or more

Unknown

How many depressive episodes has this patient suffered in the **12 months up to the latest consultation?**

0

1

2

3 or more

Unknown

When did the last depressive episode (prior to the *INDEX DATE*) start?

___/_____
mo / year

Unknown

Has this patient ever been hospitalised for **any** psychiatric condition(s)?

Yes, please specify _____

No

Unknown

In the table below, please specify if this patient has ever been hospitalised for MDD?

Ever Hospitalised for MDD	Number of hospitalisations for MDD
 Yes  No  Unknown	_____ (no. of times)

What is the date of the most recent hospitalisation for MDD?

__ / ____
 mo / year

Unknown

How long was the patient hospitalised for?

__ days

Unknown

In the table below, please specify if, according to the medical record, whether this patient has experienced psychotic episodes? Has this patient experienced psychotic manifestation in the last depressive episode?

Ever experienced psychotic symptoms during a depressive episode?	Experienced during the last depressive episode?
 Yes  No  Unknown	 Yes  No  Unknown

MDD Treatment

This section is dedicated to recording **drug treatments** received by this patient for his / her MDD in the **12 months up to [INDEX DATE]**.

In the table below, please list **ALL drug treatments for MDD** that started and ended before the initiation of Seroquel XR received by the patient in the 12 months up to [INDEX DATE]. **Please include any drug treatments for MDD noted in the patient's medical record that were prescribed either by the investigator or by other physicians.** Also, for each drug treatment, please specify information on start and end date and dosing. Please record **all changes in dose** as separate line entries.

(1) Specific drug name (generic or brand names)	(2) Start date (day/mth/year) Check for "on demand" or prn use	(3) End Date (day/mth/year)	(4) Dose (specify Unit)
	-- / / --  prn	-- / / --	_____
	-- / / --  prn	-- / / --	_____
	-- / / --  prn	-- / / --	_____
	-- / / --  prn	-- / / --	_____
	-- / / --  prn	-- / / --	_____
	-- / / --  prn	-- / / --	_____

In the table below, please list **ALL drug treatments for MDD** that were **prescribed concurrently with Seroquel XR** (including Seroquel XR) received by the patient in the 12 months up to *[INDEX DATE]*. **Please include any drug treatments for MDD noted in the patient’s medical record that were prescribed either by the investigator or by other physicians.** Also, for each drug treatment, please specify information on start and end date (if applicable), dosing and dates of dose changes.

For Seroquel XR prescriptions, please record all changes in dose as separate line entries using columns (1) – (4).

Instructions: Please answer these questions for ALL drug treatments for MDD that were prescribed by the investigator or other physicians concurrently with Seroquel XR For Seroquel XR, please record all changes in dose as separate line entries
				
Instructions: Please answer these questions only for drug treatments for MDD that were prescribed by the investigator or other physicians concurrently with Seroquel XR
		
(1) Specific drug name (generic or brand names)	(2) Start date (day/mth/year) Check for “on demand” or prn use)	(3) End Date (day/mth/year)	(4) Dose (specify Unit)	(5) Did the dose change at initiation of Seroquel XR?	(6) Most recent dose prior to [INDEX DATE] (if different than at initiation)	(7) Date of most recent dose change (day/mth/year)
	___/___/___  prn	___/___/___  Still prescribed at [INDEX DATE]	_____	 Increase  Decrease  Remained the same  Not applicable	_____  Not applicable	___/___/___  Not applicable
	___/___/___  prn	___/___/___  Still prescribed at [INDEX DATE]	_____	 Increase  Decrease  Remained the same  Not applicable	_____  Not applicable	___/___/___  Not applicable
	___/___/___  prn	___/___/___  Still prescribed at [INDEX DATE]	_____	 Increase  Decrease  Remained the same  Not applicable	_____  Not applicable	___/___/___  Not applicable
	___/___/___  prn	___/___/___  Still prescribed at [INDEX DATE]	_____	 Increase  Decrease  Remained the same  Not applicable	_____  Not applicable	___/___/___  Not applicable

Seroquel XR Treatment

Was the patient experiencing psychotic symptoms at initiation of Seroquel XR?

- Yes
- No
- Unknown

Which disorder was Seroquel XR prescribed for?

Please select all that apply

- MDD
- Schizophrenia
- Bipolar disorder
- Other – please specify _____

How many times has the investigator seen this patient since initiation of Seroquel XR?

__ visits

What is your estimate of patient adherence to the prescribed treatment regimen that included Seroquel XR for depression?

___ % of time adherent to prescribed dose(s) (range: 0 – 100%)

(Investigator assessment)

In the table below record the number of different **dosages of Seroquel XR** prescribed for this patient. Please indicate by ticking in the appropriate boxes the **different dosages** that this patient has experienced, then please enter the **number of prescriptions** for each selected dosage and the **duration (or days supply) of each prescription**.

Dosage of Seroquel XR prescribed	Number of prescription for each dosage	Duration of each prescription (in days)
 50 mg / day	__ scripts	Script 1: __ days, Script 2: __ days, Script 3: __ days, Script 4: __ days Script 5: __ days, Script 6: __ days, Script 7: __ days, Script 8: __ days
 100 mg / day	__ scripts	Script 1: __ days, Script 2: __ days, Script 3: __ days, Script 4: __ days Script 5: __ days, Script 6: __ days, Script 7: __ days, Script 8: __ days
 150 mg / day	__ scripts	Script 1: __ days, Script 2: __ days, Script 3: __ days, Script 4: __ days Script 5: __ days, Script 6: __ days, Script 7: __ days, Script 8: __ days
 200 mg / day	__ scripts	Script 1: __ days, Script 2: __ days, Script 3: __ days, Script 4: __ days Script 5: __ days, Script 6: __ days, Script 7: __ days, Script 8: __ days
 250 mg / day	__ scripts	Script 1: __ days, Script 2: __ days, Script 3: __ days, Script 4: __ days Script 5: __ days, Script 6: __ days, Script 7: __ days, Script 8: __ days
 300 mg / day	__ scripts	Script 1: __ days, Script 2: __ days, Script 3: __ days, Script 4: __ days Script 5: __ days, Script 6: __ days, Script 7: __ days, Script 8: __ days
Other 1: _____ mg / day	__ scripts	Script 1: __ days, Script 2: __ days, Script 3: __ days, Script 4: __ days Script 5: __ days, Script 6: __ days, Script 7: __ days, Script 8: __ days
Other 2: _____ mg / day	__ scripts	Script 1: __ days, Script 2: __ days, Script 3: __ days, Script 4: __ days Script 5: __ days, Script 6: __ days, Script 7: __ days, Script 8: __ days
Other 3: _____ mg / day	__ scripts	Script 1: __ days, Script 2: __ days, Script 3: __ days, Script 4: __ days Script 5: __ days, Script 6: __ days, Script 7: __ days, Script 8: __ days

Prior to initiating SEROQUEL XR, what was the patient response to their most recent prior antidepressant treatment?

		Side effects			
		None	Did not significantly interfere with Subject's functioning	Significantly interfered with Subject's functioning	Outweighed therapeutic effect (Not tolerable, Needed to stop medication)
Therapeutic effect	Marked vast improvement. Complete or nearly complete remission of all symptoms				
	Moderate improvement. Partial remission of symptoms				
	Minimal slight improvement				
	Unchanged or worse				

Unknown or Not assessed
(Investigator assessment)

When was the last consultation date for this patient?

__ / __ / ____
day / mo / year
